5.4 Inclusion/Exclusion Criteria

Inclusion Criteria for Aim 1 Veterans

1. Experience related to suicide
2. Voluntary informed consent (must be able to be given by the patient)
3. Age 18 and older
4. Fluent in English

Exclusion Criteria for Aim 1 Veterans

1. Active suicidal flag or currently hospitalized
2. Pregnant and/or incarcerated
3. Unable to provide voluntary, written informed consent for any reason (include incompetency)

Inclusion Criteria for Aim 1 Staff

1. Voluntary informed consent
2. Age 18 and older

3. Peer Specialists with experience related to suicide (Peer Specialists only)
4. Staff members with experience related to treating Veterans with experience related to suicide (Staff members only)
5. Fluent in English

Exclusion Criteria for Aim 1 Staff

1. Unable to provide voluntary, written informed consent for any reason

Inclusion Criteria for Aim 2 Veterans

1. Voluntary informed consent (must be able to be given by the patient) or voluntary informed assent with consent of a conservator if applicable
2. Age 18 and older
3. High suicide risk evidenced by a Patient Record Flag in their medical chart.
4. Fluent in English

Exclusion Criteria for Aim 2 Veterans

1. Substantially cognitively impaired as indicated by a score of 10 or higher on the Blessed Orientation, Memory, Concentration (BOMC) Test
2. Unable to provide voluntary, written informed consent for any reason (include incompetency)
3. Determined by patient's attending psychiatrist that the peer-based intervention is not appropriate due to unstable psychosis, cognitive disorder, or severe personality disorder
4. Residing outside of the VA Connecticut catchment area
5. Pregnant and/or incarcerated

Inclusion Criteria for Aim 2 Peer Specialists

1. Voluntary informed consent
2. Age 18 and older
3. Employed by the VA as a Certified Peer Specialist

Exclusion Criteria for Aim 2 Peer Specialists

1. Unable to provide voluntary, verbal consent for any reason

2. Determined by Peer Specialists' supervisor, attending psychiatrist, or other clinician that delivering the intervention is not appropriate due to prior trauma, clinical instability, or current concerns with suicide risk

5.5 Study Evaluations

Measures

The measures used to collect data for Aims 1 and 2 include data from the CPRS record as well as several rehabilitation and depression & suicide variables described in further detail below. Additionally, a study-specific form will be used to collect information about age, sex, race, ethnicity, employment, education, income, and marital status.

Rehabilitation Variables

Sheehan Disability Scale (SDS)⁶⁴. The SDS uses 3 items to measure how much work, social life, and family life are impaired by mental health symptoms. The SDS has been widely used in diverse samples,⁶⁵⁻⁶⁷ including Veterans,^{68,69} and found to be psychometrically sound and sensitive to treatment effects.

Temple University Community Participation scale (TUCP)⁷¹. The TUCP is a 26-item measure of community inclusion in the past month. The TUCP has been used in previous studies with good reliability.⁷¹⁻⁷⁴

Questionnaire about the Process of Recovery (QPR)⁷⁵. The QPR contains 15 items that measure connectedness, hope, identity, meaning, and empowerment. The QPR has demonstrated high internal and convergent validity as well as sensitivity to change.^{76,77}

Quality of Life Enjoyment and Satisfaction Questionnaire (Q-LES-Q-SF). The Q-LES-Q-SF consists of 16 items to assess life satisfaction in the past week. The Q-LES-Q-SF has been used extensively with Veterans as part of the National Health and Resilience in Veterans Study (NHRVS).

Depression and Suicide Variables

Quick Inventory of Depressive Symptoms (QIDS)⁷⁹. The QIDS consists of 16 questions to assess depression severity. The QIDS has demonstrated high reliability, validity, and sensitivity to treatment change,⁸⁰, including among Veterans.⁸¹

Columbia-Suicide Severity Rating Scale (C-SSRS)⁸². The C-SSRS is used to assess suicidal ideation (past 30 days) and behaviors (past 3 months). Suicide ideation items include: (1) wish to be dead, (2) non-specific suicidal thoughts, (3) suicidal thoughts with methods, (4) suicidal intent, and (5) suicidal intent with plan. The suicide behavior subscales include: (1) attempts (actual, aborted, interrupted), (2) preparatory behavior, and (3) non-suicidal self-injurious behavior. We will also use two measures of psychosocial variables that potentially mediate suicide risk and are hypothesized to be impacted by PSs.

Interpersonal Needs Questionnaire (INQ)⁸³. The INQ uses 15 items to measure two underlying motives for suicidal desire (i.e., perceive burden and thwarted belonging). The INQ has established validity and reliability,⁸⁴ including on Veterans.⁸⁵

Suicide Cognitions Scale (SCS)⁸⁶. The SCS contains 18 items that assess thoughts of unloveability, unsolvability, and unbearable. The SCS has strong psychometric qualities in diverse samples (including Veterans) with incremental validity to predicting suicidal behavior beyond depression, INQ scores, prior attempts, and suicidal ideation.^{87,88}

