2.0 Introduction

Background and Rational

Veteran suicide is a public health crisis: According to the most recent VA National Suicide Data Report: 2005-2016,²⁹ the Veteran suicide rate increased by 26%, as compared to 21% for non-Veteran adults. Although suicide rates rose more sharply for non-VHA Veterans (26%) than for VHA patients (14%), the suicide rate among VHA patients is higher than Veterans who are not receiving VHA care.

Suicidal ideation is a frequent precursor to non-fatal and fatal suicide attempts.³⁰ Suicidal ideation is reported by 3%-52% of Veterans, depending on the time frame (e.g., past month vs. current) and population (e.g., general community, primary care, or urgent care psychiatric clinic).³¹⁻³³ Similar rates for suicide attempts are reported by Veterans (2%-48%). Despite increased relative risk of suicide among persons expressing suicide ideation, the absolute risk of suicide is low.^{34,35}

[figure not shown]
Care for high-risk Veterans features increased contact but lacks a focus on key life domains: VHA patients who attempt suicide, report serious suicidal ideation, or exhibit other warning signs of acute suicide risk have a Patient Record Flag (PRF) placed in their medical record for no less than 90-days. The VHA maintains a list of

active PRFs to alert all staff that increased follow-up and case management are required.³⁶ Patients with PRFs must have at least 4 clinical contacts within the first 30 days after the flag is placed or following discharge from the hospital. During these 30 days, they must be also assessed four times. Clinical care focuses primarily on safety planning, use of the Veterans Crisis Line, stepped-up mental health care, and additional case management support from the Suicide Prevention Coordinator,³⁷ rather than directly addressing needs in other life domains. Recent evaluations of the VHA suicide prevention initiatives observe deficits in tracking, safety planning, and care practices for high suicide risk Veterans.³⁸

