The PREVAIL intervention consists of weekly interactions over the course of 3-months using a flexible approach to accommodate Veteran's preferences and recovery needs over the course of the typical duration of a PRF. During weeks 1 and 2 of the intervention, Veterans meet twice weekly with a PS. During weeks 3 through 8, meetings are once weekly. During weeks 9 through 12, meetings typically occur once every other week. Over the course of the 3-month intervention, this approach bolsters the development of a strong therapeutic alliance in the beginning (weeks 1-2), followed by active teaching and reinforcing new skills (weeks 3-8), and then culminating with mastering new skills and preparing the Veteran for active self-management and sustained recovery. For a small number of PREVAIL participants, an additional 3 sessions were added over the span of the last 4 weeks to provide additional time to prepare for the end of the therapeutic relationship. A similar approach will be used for the current pilot.

Meetings between PSs and Veterans will be approximately 45-60 minutes and occur primarily in the community, home, clinic, by telephone, or VA-approved video calling platform (e.g. VVC, WebEx). Session content will be rooted in PSs offering nonjudgmental empathic support, active listening, and constructive disclosure and role modeling. A primary focus will be helping patients with PRFs to identify and strengthen connections with informal supports and participation in activities in their community that will enable them to feel more worthwhile as individuals and hopeful about their future.

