Veterans in both the pre-pilot and formal pilot will each meet with research staff for a Baseline Visit, Post-Intervention Visit, and a 3-Month Follow-Up Visit. All participants will also be invited to participate in an in-depth qualitative interview shortly after their 3- month follow-up assessments to assess their views of the intervention, including barriers, strengths, and recommended changes. All qualitative interviews will be recorded and transcribed. During the interviews, participants will be encouraged to avoid using names. If any name is recorded, it will be omitted from the written transcript (i.e., the transcript may read [name] in place of the actual name). Only the study team will have access to data collected by questionnaires, interviews, and medical record data.

Risks and Risk Minimization

Needs Assessment (Aim 1): There are no foreseeable physical or medical risks in this portion of the project. However, potential participants will be informed of the general nature of the study, what their involvement entails, the risks/benefits, and limitations to confidentiality prior to providing informed consent. The site PI for VA Connecticut and Co-I will contact key staff and make arrangements for interviews. Three Veterans will be identified pursuant to a HIPAA waiver, and a letter will be mailed to them inviting their participation.

We will minimize risks to interview participants by thoroughly explaining to them that participation in the project is strictly voluntary and that the decision not to participate will have no bearing on their employment. Individual names of employment settings and associated responses will not be provided to any other agency. In reports, publications, or presentations using project research data, we will report the data in aggregate form and/or change names and disguise the identity of any individual we describe or quote for purposes of illustration or example.

Pre-and Formal Pilot Testing (Aim 2): A potential risk to study participants is clinical deterioration of their mental health and/or an increase in suicidal thoughts or behaviors

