5.2 Recruitment Methods

Recruitment-Aim 1

We will recruit a diverse group of 12 individuals for the Needs Assessment phase of the project to inform the adaptation of PREVAIL. This group will be comprised of Veterans (3), Peer Specialists (3), Providers from behavioral health, inpatient and outpatient psychiatry, and other relevant departments (4), and Clinical Directors (2).

We will obtain a waiver of HIPAA authorization to identify Veterans to participate in the Needs Assessment. Once these Veterans are identified, they will be mailed a letter informing them about and requesting their participation in the Needs Assessment interviews. A member of the study team will follow-up with a telephone call approximately one week after the letter is sent. The team members will attempt to reach the Veterans by phone 3 times and will leave no more than two messages. Providers, clinical directors, and Peer Specialists will either be sent an email or will be verbally invited in person to participate in the Needs Assessment.

Recruitment for the Steering Committee

The Steering Committee will be comprised of researchers and VHA leadership. The site PI will identify appropriate VA staff and other providers and will contact them by phone or email.

Recruitment-Aim 2

We will recruit 4-6 Peer Specialists who are currently working in VA Connecticut Healthcare System (VACT) to receive training in the PREVAIL model and to deliver the intervention for the pre- and formal pilot. All of the selected Peer Specialists have been trained and certified, with multiple years of clinical experience working with Veterans in recovery, including those who have been at some point 'flagged' for suicide risk.

We will include a sample of up to 24 VHA patients identified as being high-risk for suicide at the VA Connecticut Healthcare System (VACT) to receive the pilot intervention as an adjunct to usual care. Patients will be considered high suicide risk if they have a Patient Record Flag (PRF) in their medical chart for a recent suicide attempt, serious suicidal ideation, or other warning signs of acute suicide risk. The VACT Suicide Prevention Coordinator maintains a list of patients with active PRFs. This population is targeted because they are at greatest risk for suicide and therefore most in need of intervention.

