In addition to reaching out to Veterans on the high-risk list, we also will engage Veterans via the New Haven VA psychiatric Emergency Room, inpatient units, and individual New Haven clinicians. Specifically, we will engage with staff to find out if any Veteran has received a score on the Columbia-Suicide Severity Rating Scale Screen of 3 or greater in the last three months. This measure is used commonly in the VA. Such a score is known to be an optimal cut off score for identifying individuals who would likely attempt suicide. In a recent study of nearly 19000 patients, those scoring over the cut-off of ≥ 3 had almost four times the odds of dying by suicide within 1 week and 1 month, respectively, and doubled the odds of dying within a year⁹⁰. We will also engage with individual clinicians to assess whether any of their patients have recently received a score of ≥ 3 on the Columbia measures. In addition, we will ask these staff about any Veteran who made a suicide attempt in the last three months. Thus, the additional recruitment criteria we are adding will be:

- Any Veteran from the New Haven VA psychiatric Emergency Room, the New Haven inpatient units, or from individual New Haven clinicians who received a score on the Columbia-Suicide Severity Rating Scale Screen of 3 or greater in the last three months
- Any Veteran from the New Haven VA psychiatric Emergency Room, the New Haven inpatient units, or from individual New Haven clinicians who made a suicide attempt within the last three months

Each month, there are approximately 105 VHA patients with PRFs for suicide risk at the CT VA campuses. In addition to those Veterans with a PRF, we also will be recruiting those Veterans with suicidal ideation or attempts. This pool of Veterans should be sufficient to recruit participants for the pre-pilot (n=12) and formal pilot (n=12). Assuming a 75% retention rate (as achieved in [name] PREVAIL pilot)¹⁵ this will yield a final sample of 18 patients with outcome data at post-intervention and 3-month follow-up. This sample size will yield reasonably precise estimates of feasibility in terms of actual rates of recruitment, retention, compliance/fidelity to intervention, and completion of outcome assessments.

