Once eligible Veterans are identified, they will be mailed a letter along with a study information sheet, inviting them to participate in Aim 2 of study. A member of the study team will follow-up with a telephone call approximately one week after the letter is sent if they do not hear back from the Veterans. The team members will attempt to reach

the Veterans by phone 3 times and will leave no more than two messages.

Additionally, the site PI will work with providers of eligible Veterans seeking their help in recruiting these Veterans into the study and will also provide them with a study information sheet. Once the provider identifies an eligible Veteran, they will discuss the study with the Veteran and if the Veteran is interested in hearing more about the study, the provider will call the study staff with the Veteran present or will share the number of the study staff with the Veteran so that they may call the study staff at their own convenience. In the event that the provider facilitates the phone call with study staff, the provider will step out of the room to give the Veteran a chance to learn more about the study. for this to occur. If a provider or research staff cannot reach the Veteran by phone, they will follow-up with a CIRB-approved letter as described above.

Version 4.0 Suicide Prevention Protocol Page **20** of 36

Payments

Veterans who participate in the Needs Assessment interview will receive \$25 for their time and effort. Study participants will receive \$25 upon completion of each assessment interview (baseline, post-intervention, 3-month follow-up), for a total of up to \$75. Additionally, Veterans who participate in the one-time interview will receive \$25 for their time and effort.

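### For Veterans who enter after a recent suicide attempt, the baseline C-SSRS behaviour window usually contains that attempt and the post-intervention window usually does not, so attempts are expected to fall without any intervention effect

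*Protocol*

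**What the plan says.** - **Measurement.** Protocol section 5.5: "The C-SSRS is used to assess suicidal ideation (past 30 days) and behaviors (past 3 months"). Attempts are among the behaviour subscales. No different look-back is given for later visits.
- **Entry.** Section 5.2 recruits patients with a Patient Record Flag "for a recent suicide attempt, serious suicidal ideation, or other warning signs of acute suicide risk". It adds Veterans from the psychiatric emergency room, inpatient units or "individual New Haven clinicians who made a suicide attempt within the last three months", and a further route through a C-SSRS screen score.
- **Delay before baseline.** An invitation letter is followed by a call about "one week after the letter is sent if they do not hear back from the Veterans", with up to three call attempts. No maximum delay is set. Section 2.0 says a flag is "placed in their medical record for no less than 90-days".
- **Timing.** The intervention lasts 3 months; section 5.1 lays it out to week 12 ("During weeks 9 through 12, meetings typically occur once every other week"). Each Veteran has "a Baseline Visit, Post-Intervention Visit, and a 3-Month Follow-Up Visit". All receive the intervention.
- **Analysis.** Section 5.6 plans descriptive statistics and confidence intervals for each measure at each assessment, with plots to look for trends linked to the intervention. It excludes hypothesis testing because of the small sample, and says the results will inform power and sample size for a larger trial. The SAP classifies each participant's pre-to-post change on each outcome measure by the Reliable Change Index (RCI), without listing the measures.

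**The concern.** For one group of entrants, the event that brought them into the study is also scored at the first visit. Entry and the baseline score look back over nearly the same three months. The post-intervention score looks back over a new three months in which no attempt is required. A drop is therefore built into the pre-post comparison for these Veterans, and without a control arm nothing in the data separates it from an intervention effect.

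The section 5.6 caveat concerns imprecision. This is bias, and a larger sample would not remove it. At stake is how tables and plots of attempts are read in a suicide prevention pilot. If the change were carried forward, the planning of the larger trial would also be affected.

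**Working it through.** **1. The plan's own figure.** Section 5.2: 24 recruited × 75% retained = 18 with outcome data. This reproduces. The argument does not depend on it, but 18 is used below.

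**2. Inputs.**
- From the documents: a 3-month window, W, taken as 90 days; at least 84 days (12 weeks) from baseline to the post-intervention visit.
- Assumed: lag L from identification to baseline of 0-42 days; ordinary 3-month attempt probability r of 5-30%; attempts at a constant (Poisson) rate, with no intervention effect.

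**3. Does each window contain the qualifying attempt?** Take its timing as uniform over the 90 days before identification.
- Baseline window: (90 − L)/90 = 100% at L = 0, 84% at 14 days, 69% at 28 and 53% at 42.
- Post-intervention window, visit at day 84: max(0, (90 − 84 − L)/90) = 6.7% at L = 0, and 0 at 14 days or more. With a visit at day 90 it is 0 throughout.

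So *usually* is the right word for both windows.

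**4. No-effect fall among attempt entrants.** An entrant has no attempt in the baseline window only if the sole attempts before identification fell in the earliest L days and none occurred during the lag. Hence the share with an attempt in the baseline window is

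B = 1 − [(1 − r)/r] × [1 − (1 − r)^(L/90)].

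The post-intervention share is r (visit at day 90), so the fall is B − r.

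| Lag | r = 5% | r = 30% |
|---|---|---|
| 0 days | 100% to 5%: 95.0 points | 100% to 30%: 70.0 points |
| 14 days | 84.9% to 5%: 79.9 | 87.4% to 30%: 57.4 |
| 28 days | 69.9% to 5%: 64.9 | 75.5% to 30%: 45.5 |
| 42 days | 55.1% to 5%: 50.1 | 64.2% to 30%: 34.2 |

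A separate simulation with 91-day windows agrees: at L = 14, 85% to 5% for r = 5% and 87% to 30% for r = 30%. With zero lag and the post visit at day 84, where the windows overlap most, it still gives 100% to 12% (r = 5%) and 100% to 35% (r = 30%).

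**5. Whole sample.** Let m of 18 completers be attempt entrants, and suppose the rest have probability r at both visits. The baseline count is mB + (18 − m)r and the post-intervention count is 18r. At L = 14 and r = 10%, B = 85.4%, and the post-intervention count is 1.8. For m = 0, 3, 6 and 9 the baseline counts are 1.8, 4.1, 6.3 and 8.6. The documents give no value for m, so these are illustrations only.

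**6. Would subtracting the qualifying attempt at baseline repair this?** No. With μ = −ln(1 − r) and zero lag, the share of attempt entrants with a second attempt in the window is [r − μ(1 − r)]/r.
- r = 10%: μ = 0.1054, giving 5.2% at baseline against 10% post-intervention.
- r = 30%: μ = 0.3567, giving 16.8% against 30%.

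Subtraction therefore produces an apparent rise with no effect.

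**The case against.** The strongest reply is that the plan makes no efficacy claim. Section 5.6 says the study is not determining effectiveness, excludes hypothesis tests and calls outcome comparisons unreliable. The next study is to be randomized, and its control arm would share the selection effect. This limits the harm but does not remove it: the same section still plans per-visit summaries and plots of trends linked to the intervention, and its stated reason for caution would not alert a reader to bias.

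The share of attempt entrants is unknown and could be small, since flags also cover ideation and other warning signs and the C-SSRS screen is a further route. That stands, so no whole-sample size is claimed. Uniform or constant-rate timing is also an assumption; it affects the size of the fall more than its direction.

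A reader might infer more than the documents support:
- *That the SAP will classify behaviours by RCI.* It says each outcome measure but lists none, and section 5.5 describes behaviours as event categories without a score. The point is conditional.
- *That the larger trial's effect size will be inflated.* Section 5.6 does not say which quantities will be used.
- *That the chart-review outcome in the Abstract has the same artefact.* Its look-back is not stated.
- *That ideation items, the other scales, or the step from post-intervention to 3-month follow-up are affected.* The window argument shows nothing for these.

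**Conclusion.** The concern holds for Veterans who enter after an attempt in roughly the last three months. For them, the planned pre-post display of attempts is expected to fall with no intervention effect: by about 57-80 points at a 14-day lag and 45-65 at 28 days, assuming a constant rate and r of 5-30%. The direction was the same in every scenario examined. The fall in the whole sample cannot be computed from the documents, and it is zero if nobody enters this way.

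This is a problem of interpretation in a descriptive pilot. The progression criteria in the Abstract (over 50% enrolment, over 70% follow-up) do not depend on it. It should be corrected because the remedy is cheap and a spurious fall in attempts is easily misread.

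**What to change.** 1. Report C-SSRS behaviours as post-baseline counts with exact confidence intervals. Show baseline behaviours only as a description of the sample, not as the start of a pre-post trend. Do not simply subtract the qualifying event from the baseline count.
2. List the SAP's outcome measures. If behaviours are among them, exempt them from pre-post RCI classification.
3. Record and tabulate each participant's entry route and the type and date of the qualifying event, so that the affected share and the lag are known.
4. State that the pre-post change in behaviours will not be used as an effect size for the larger trial.
5. State the look-back for the chart-review outcome. It needs the same care only if that period includes the qualifying event.

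The cost is protocol and SAP wording plus a few entry-data items, with no new visits or measures. The SAP is written in the past tense; even if analysis has begun, the reporting changes remain possible. The downside is a less favourable pre-post picture and wide intervals: 0-18.5% for 0 of 18, and 1.4-34.7% for 2 of 18.

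Separately, section 5.4 gives as its only high-risk criterion "High suicide risk evidenced by a Patient Record Flag in their medical chart", while section 5.2 adds the attempt and screen-score routes. Those passages must be reconciled.
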